#### 7.3.6.7 Serious Adverse Events

An SAE is any AE occurring from Screening through final study visit (Day 365), at any dose that results in any of the following outcomes:

- Death
- A life-threatening adverse drug experience
- Inpatient hospitalization or prolongation of existing hospitalization
- A persistent or significant disability/incapacity
- A congenital anomaly/birth defect

Important medical events that may not result in death, be life threatening, or require hospitalization may be considered an SAE when, based upon appropriate medical judgment, they may jeopardize the patient and may require medical or surgical intervention to prevent any of the outcomes listed in this definition. Examples of such medical events include allergic bronchospasm requiring intensive treatment in an emergency room or at home, blood dyscrasias or convulsions that do not result in inpatient hospitalization, or the development of drug dependency or drug abuse.

Note: SAEs require immediate reporting to [REDACTED]. See “Reporting Serious Adverse Events” below for details.

### 7.3.6.8 Reporting Serious Adverse Events

In the event of any SAE reported or observed during the study, whether or not attributable to the study drug, site personnel will report it to [REDACTED] within 24 hours of the knowledge of the occurrence.

To report the SAE, complete the SAE form electronically in the electronic data capture (EDC) system for the study. When the form is completed, [REDACTED] personnel will be notified electronically and will retrieve the form. If the event meets serious criteria and it is not possible to access the internet, send an email to [REDACTED] at [REDACTED] or call the [REDACTED] (phone number listed below), and fax/email the completed paper back-up SAE form to [REDACTED] (contact information listed below) within 24 hours of awareness. When the EDC system becomes available, the SAE information must be entered within 24 hours of the system becoming available. Incoming reports are reviewed during normal business hours.

#### Safety Contact Information:

[REDACTED]

The Investigator is required to submit SAE reports to the Institutional Review Board (IRB)/Independent Ethics Committee (IEC) in accordance with local requirements. All investigators involved in trials using the same investigational product will receive any safety alert notifications for onward submission to their local IRB/IEC as required. All reports sent to investigators will be blinded.

#### Follow-Up Reports

The Investigator must continue to follow the patient until the SAE has resolved or until the condition becomes chronic in nature, stabilizes (in the case of persistent impairment) or the patient dies.

Within 24 hours of receipt of follow-up information, the Investigator must update the SAE form electronically in the EDC system for the study and submit any supporting documentation (e.g., patient discharge summary or autopsy reports) to [REDACTED] personnel via fax or e-mail. If it is not possible to access the EDC system, refer to the procedures outlined above for initial reporting of SAEs.

#### **7.4 Efficacy Variables**

Serum phosphorus will be measured at all study visits. The primary efficacy variable will be the change in s-P from the end of the 26-week treatment period (Visit 13) to the end of the randomized withdrawal period or the endpoint visit for this period. The primary efficacy analysis will be based on the difference between the tenapanor treatment and placebo treatment group in the responder population. A responder is a patient that had a serum phosphorus decrease of  $\geq 1.2$  mg/dL from enrollment (Day 1) to the end of the 26-week treatment period (Visit 13).

The following are the secondary variables:

- Patients reaching serum phosphorus goal levels defined as  $< 5.5$  mg/dL during the 26-week treatment period
- Ca x P product
- iFGF23 (intact) and cFGF23 (c-terminus)
- Kidney Disease and Quality of Life survey (KDQOL)
  - Kidney Disease and Quality of Life™ (KDQOL™-36) (Copyright © 2000 by RAND and the University of Arizona)
- Dialysis Symptom Index survey (DSI)
  - The University of Pittsburgh Medical Center, VA Pittsburgh Healthcare System (Weisbord et al. J Pain Symptom Manage, 2004:27, 226-40.)

#### **7.5 Exploratory Variables**

The following exploratory variables will be collected at specified times to investigate the relationship with drug efficacy.

- Exploratory biomarker analyses (potentially in future)

Plasma and serum for future exploratory research into biomarkers related to the cardio-renal disease area and/or related to the response (i.e. distribution, safety, tolerability and efficacy) to tenapanor.

## 8 METHODOLOGY/STUDY VISITS

### 8.1 Screening (Day -21), Visit 1

At the Screening visit, the Investigator will inform each prospective patient of the nature of the study, explain the potential risks, and obtain written informed consent from the patient prior to performing any study-related procedures.

Screening evaluations will consist of the following:

- Informed consent (may be completed day(s) before Screening visit, if needed)
- Inclusion and exclusion criteria ([Section 5](#))
- Demographics
- Height and weight (pre-dialysis)
- Medical/surgical history
- Phosphate binder used and dose
- KDQOL survey
- DSI survey (for English speakers only)
- Kt/V (most recent measurement prior to screening)
- Physical examination ([Section 7.3.1](#))
- Vital signs (pre-dialysis) ([Section 7.3.2](#))
- ECG evaluation ([Section 7.3.3](#))
- Clinical laboratory tests (pre-dialysis) ([Section 7.3.4](#))
  - Serum chemistry
  - Hematology
  - Coagulation profile (if applicable)
- FSH test and serum pregnancy test will be performed on all females
- HIV, hepatitis B and C tests
- FGF-23, Ca x P product and exploratory biomarker sample (pre-dialysis)
- Begin collecting adverse events
- Start washout of phosphate binders
- Prior/concurrent medications

Patients will be instructed not to change any concomitant medications without the approval of the Investigator. The results of the screening evaluations (available at that time) must meet the inclusion/exclusion criteria for the patient to continue to the wash-out period.

Rescreening will be allowed for subjects who screen fail at Visit 1 due to serum phosphorus levels outside of the protocol inclusion range (<4.0 or >8.0 mg/dL) and based on the criteria in Section 5.3.

## **8.2 Wash-out Period (Days -14, -7, and -1), Visits 2, 3 and 4**

The period which patients are off binders can last up to 4 weeks. If at Visit 2, 3 or 4 (Days -14, -7 or -1) a patient's serum phosphorus is  $\geq 6.0$  mg/dL and not more than 10.0 mg/dL and there has been a  $\geq 1.5$  mg/dL increase since the screening visit (Visit 1) they can proceed to Visit 5 for enrollment; otherwise patients should proceed to the next visit. At Visit 4, if a patient's serum phosphorus does not meet the above inclusion criteria, the patient is screen failed.

The following procedures should occur at washout visits

- Review of inclusion /exclusion criteria
- Changes to medical/surgical history
- Changes to Prior/concurrent medications
- Vital signs (pre-dialysis)
- Serum phosphorus (pre-dialysis)
- Adverse event reporting

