- d AEs and SAEs will be collected from consenting to the end of study.
- e Kt/V should be the most recent historical value prior to screening.
- f Height will also be measured at the screening visit
- g In the randomized withdrawal period, patients in the tenapanor group only are randomized 1:1 to either stay on current treatment of tenapanor or receive a matched placebo; based on withdrawal criteria, patients may enter the safety assessment period at any visit.
- h If the laboratory evaluations from the wash-out period deem the patient ineligible for the study, the site must inform the patient and tell them to take their phosphate binders.
- i s-Phosphorus sample collected at visits when safety labs are not collected.
- j KDQoL (KDQoL™-36), Kidney Disease and Quality of Life survey. DSI, Dialysis Symptom Index survey is for English speakers only and is not validated in other languages.
- k Randomization #1 is 3:1, tenapanor: active control. Randomization #2 is 1:1 from the tenapanor group only to tenapanor: placebo. Patients in the active control group will receive sevelamer carbonate for the entire 52-week study period.
- l Drug accountability will be performed for both tenapanor and the active control.
- m Visits 14, 16 and 18 are not done for subjects randomized into the active control group.
- n Patients should be randomized by the week after meeting s-P washout criteria; total period off binder must not be greater than 4 weeks.

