## 4 STUDY DESIGN

### 4.1 Design Summary

The study consists of a screening visit, a phosphate binder-free wash-out period of up to four weeks, a 26-week treatment period, an up to 12-week placebo-controlled, randomized withdrawal period during which patients are randomized 1:1 to either remain on the tenapanor dose they are taking at the end of the 26-week treatment period or receive placebo, followed by an open label safety extension period for a total treatment period of up to 52 weeks. An active control group, for safety analysis, will receive sevelamer carbonate, open label, for the entire 52-week study period (see [Section 2.3](#)).

The screening visit (Visit 1) and all other visits in the study must be scheduled after a short dialysis interval (only for HD patients; e.g., Wednesday or Friday for patients on a MWF schedule and Thursday or Saturday for patients on a TThS schedule). Body weight, vital signs and blood collections for laboratory assessments **must** be performed pre-dialysis. All other assessments may be performed pre-, during, or post-dialysis but should be performed at the same time at each visit. For PD patients, visits should be performed on the same day each week, if possible. For all patients, serum phosphorus measured at the screening visit must be  $\geq 4.0$  and  $\leq 8.0$  mg/dL or patients to be eligible to enter the wash-out period.

The wash-out period will begin immediately after the screening visit. Serum phosphorus will be measured weekly (pre-dialysis after a short interval for HD patients) during the wash-out period to determine if the patient meets inclusion criteria for enrollment into the study.

The study visits during the wash-out period for HD patients should be scheduled after the first short interval in the week to ensure data is available before a possible randomization, which could then take place after the second short interval in the week. Otherwise the randomization visit will be scheduled the following week after the first short dialysis interval; therefore, the total length of phosphate binder wash-out may be up to 4 weeks.

The wash out period will be a minimum of 1 week and must not exceed 4 weeks. Patients should be randomized by one week after meeting s-P washout criteria (after visit 2, 3 or 4); the total washout period must not be greater than 4 weeks.

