### 5.1 Inclusion Criteria

A patient will be eligible for study participation if he/she meets the following criteria:

1. Signed and dated informed consent prior to any study specific procedures.
2. Males or females  $\geq$  18 years of age.
3. Females must be non-pregnant, non-lactating and fulfilling one of the following:
  - a. Post –menopausal defined as amenorrhea for at least 12 months following cessation of all exogenous hormonal treatments and with follicle stimulating hormone (FSH) levels in the laboratory defined post-menopausal range.
  - b. Documentation of irreversible surgical sterilization by hysterectomy, bilateral oophorectomy or bilateral salpingectomy, but not tubal ligation.
  - c. Use of acceptable contraceptive method: IUD with spermicide, a female condom with spermicide, contraceptive sponge with spermicide, an intravaginal system (e.g., NuvaRing®), a diaphragm with spermicide, a cervical cap with spermicide, or oral, implantable, transdermal, or injectable contraceptives, sexual abstinence, or a sterile sexual partner.
4. Males must agree to avoid fathering a child (or donating sperm), and therefore be either sterile (documented) or agree to use, from the time of enrollment until 45 days after end of study, one of the following approved methods of contraception: a male condom with spermicide, a sterile sexual partner, use of an IUD with spermicide by female sexual partner, a female condom with spermicide, contraceptive sponge with spermicide, an intravaginal system (e.g., NuvaRing®), a diaphragm with spermicide, a cervical cap with spermicide, or oral, implantable, transdermal, or injectable contraceptives.
5. Chronic maintenance hemodialysis 3x/week for at least 3 months or chronic maintenance peritoneal dialysis (PD) for a minimum of 6 months. If modality of dialysis has changed patient must meet one of the two dialysis criteria above and been on the new modality of dialysis for a minimum of one month.
6. Stable vascular access as assessed by Investigator if on HD.
7.  $Kt/V \geq 1.2$  at most recent measurement prior to screening.
8. Prescribed and taking at least 3 doses of phosphate binder per day. The prescribed dose should have been unchanged during the last 3 weeks prior to screening.

9. Serum phosphorus levels should be between 4.0 and 8.0 mg/dL (inclusive) at screening analyzed at the central laboratory used in the study.
10. Intentionally left blank.

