### 5.4 Patient Withdrawal

Patients are free to discontinue the study at any time, for any reason, and without prejudice to further treatment. The Investigator may remove a patient if, in the Investigator's judgment, continued participation would pose unacceptable risk to the patient or to the integrity of the study data. Some study specific discontinuation criteria will also apply to study participants receiving tenapanor or placebo:

- **Hypophosphatemia:** Serum phosphorus  $\leq 2.5$  mg/dL at any time.
- **Hyperphosphatemia:**
  - Serum phosphorus  $\geq 10.0$  mg/dL any time after Week 2 of the 26-week treatment period
  - Serum phosphorus  $\geq 9$  mg/dL for two consecutive visits after Week 2 during the 26-week treatment or safety extension period
  - Serum phosphorus  $\geq 9$  mg/dL during the randomized withdrawal period

Patients discontinued from the randomized withdrawal period will be offered the opportunity to enter the open-label safety assessment period or be discontinued from the study and return to standard of care.

Patients in the active control group, receiving sevelamer carbonate do not have specific discontinuation criteria; they will be treated based on standard of care using the package insert for guidance.

A patient who discontinues will always be asked about the reason(s) for discontinuation and the presence of any AEs. The Investigator will record the reason for early withdrawal in the eCRF.

If a patient discontinues the study, all visit procedures for Visit 23 will be completed, if possible.

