### 7.3.5 Analysis of Clinical Laboratory Tests

A certified laboratory will be used to process and provide results for the clinical laboratory tests. The baseline laboratory test results for clinical assessment for a particular test will be defined as the last measurement prior to the initial dose of study drug or active control.

For any laboratory test value outside the reference range that the Investigator considers clinically significant, the Investigator will:

- Repeat the test to verify the out-of-range value.
- Follow the out-of-range value to a satisfactory clinical resolution.
- Record as an AE any laboratory test value that (1) is confirmed and the Investigator considers clinically significant, or (2) that requires a patient to be discontinued from the study, or (3) that requires a patient to receive treatment, or (4) fulfills one or more SAE criteria.

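### The wash-out rule in Section 8.2 sends a patient with serum phosphorus above 10.0 mg/dL at Visit 2 or 3 on to the next visit off binders, with no numeric upper stop.

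*Combined protocol and SAP*

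**What the plan says.** Section 8.2 sets three conditions for enrollment from Visit 2, 3 or 4: s-P at least 6.0 mg/dL, s-P not above 10.0 mg/dL, and a rise of at least 1.5 mg/dL since screening. Patients who meet them "they can proceed to Visit 5 for enrollment; otherwise patients should proceed to the next visit". At Visit 4, not meeting them is a screen failure. The section names no earlier exit on s-P.

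Other provisions bear on the same patient:

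- **Section 5.1, criterion 9:** "Serum phosphorus levels should be between 4.0 and 8.0 mg/dL (inclusive) at screening".
- **Section 1.3, footnote h:** if wash-out laboratory results make the patient ineligible, "the site must inform the patient and tell them to take their phosphate binders". It gives no s-P value and no visit.
- **Section 5.4:** the numeric s-P limits are introduced with "Some study specific discontinuation criteria will also apply to study participants receiving tenapanor or placebo". One of them is a single value of at least 9 "mg/dL during the randomized withdrawal period". The section also lets the investigator remove a patient where "continued participation would pose unacceptable risk to the patient or to the integrity of the study data".
- **Section 7.3.5:** for an out-of-range result judged clinically significant, the investigator repeats the test and must "Follow the out-of-range value to a satisfactory clinical resolution".
- **Section 4.1:** "The wash out period will be a minimum of 1 week and must not exceed 4 weeks".
- **Section 5.2, exclusion 1:** this uses a 10.0 mg/dL limit, but only for values on binders in the 3 months before screening.

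**The concern.** The instruction to go to the next visit makes sense for a patient whose s-P has not risen far enough, because more time off binders may bring it into range. The same words also govern a patient whose s-P is already too high, for whom more time off binders works in the wrong direction. Going to the next wash-out visit means staying untreated, although the sentence does not say so in those terms.

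Two things are at stake. The first is safety: the written default prolongs untreated hyperphosphatemia above the protocol's own enrollment ceiling. The second is consistency. With 70 to 95 sites planned (Synopsis), some may restart binders at once under footnote h, while others may follow Section 8.2 literally and wait for Visit 4.

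**Working it through.** The protocol gives no figure on this point, so there is nothing to reproduce. The check is of the rule's logic, followed by the time it adds.

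**1. Apply Section 8.2 as written.** Take a screening s-P of 8.0 mg/dL, the highest allowed.

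| s-P (mg/dL) | Rise | Visit 2 | Visit 3 | Visit 4 |
|---|---|---|---|---|
| 5.5 | none | to Visit 3 | to Visit 4 | screen failure |
| 9.5 | 1.5 | enroll | enroll | enroll |
| 10.0 | 2.0 | enroll | enroll | enroll |
| 10.1 | 2.1 | to Visit 3 | to Visit 4 | screen failure |
| 14.0 | 6.0 | to Visit 3 | to Visit 4 | screen failure |

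Values of 10.1 and above follow the same path at screening values of 4.0 and 6.0. The rule treats 5.5 and 14.0 identically.

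**2. Can more wash-out serve its purpose above 10.0?** The smallest possible rise exceeds 10.0 − 8.0 = 2.0 mg/dL, which is more than the required 1.5. The value also exceeds 6.0. Both lower criteria are therefore met already, and only the ceiling fails. The patient can qualify later only if s-P falls without treatment.

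**3. Look for another numeric stop.**
- The Section 5.4 limits cover patients receiving tenapanor or placebo, and a wash-out patient receives neither.
- Exclusion 1 concerns on-binder values before screening.
- Footnote h has no threshold.
- Sections 5.4 (removal) and 7.3.5 rest on judgment.
- The 4-week cap limits time, not level.

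None of these is a number that ends wash-out early.

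**4. Added days off binders.** Visits 2, 3 and 4 fall on Days −14, −7 and −1, each ±2 (Section 1.3). The windows, counted arithmetically, are [−16, −12], [−9, −5] and [−3, +1].

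| Interval | Scheduled | Shortest | Longest |
|---|---|---|---|
| Visit 2 to 3 | −7 − (−14) = 7 | −9 − (−12) = 3 | −5 − (−16) = 11 |
| Visit 2 to 4 | −1 − (−14) = 13 | −3 − (−12) = 9 | +1 − (−16) = 17 |
| Visit 3 to 4 | −1 − (−7) = 6 | −3 − (−5) = 2 | +1 − (−9) = 10 |

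**5. How often? Illustration on assumptions only.** The documents give no distribution for the wash-out rise. Assume it is normal, with mean 1.0 to 2.0 mg/dL and SD 1.0 to 1.6. The upper SD is borrowed from Section 9.2, where it describes a different quantity, the change during randomized withdrawal. Then P(s-P > 10.0) = 1 − Φ((10.0 − screening − mean rise)/SD).

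| Screening s-P | Mean 1.0, SD 1.0 | Mean 2.0, SD 1.6 |
|---|---|---|
| 6.0 | 1 − Φ(3.00) = 0.001 | 1 − Φ(1.25) = 0.106 |
| 7.0 | 1 − Φ(2.00) = 0.023 | 1 − Φ(0.625) = 0.266 |
| 8.0 | 1 − Φ(1.00) = 0.159 | 1 − Φ(0) = 0.500 |

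The last cell is 0.500 only because the assumed mean rise lands exactly on the threshold. The pattern is more useful than the values: the problem gathers near the top of the screening range.

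**The case against.** The best reply is that the protocol already contains the means to act. Section 8.2 has the site review the inclusion and exclusion criteria at every wash-out visit, criterion 11 supplies the 10.0 mg/dL ceiling, and footnote h then restarts binders. A site could combine these at Visit 2. That reading is open, and for this reason the text is ambiguous rather than contradictory. It is not compelled, however: criterion 11 allows qualification after 1, 2 or 3 weeks, and Section 8.2 declares failure on s-P only at Visit 4.

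Other objections:

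- **A high value may be spurious, and Visit 3 is itself a retest.** This is fair. A patient at 10.1 could qualify a week later. It argues for a prompt confirmatory repeat rather than a default wait of about a week.
- **Nobody can act until the result is back, so the day counts are too long.** The reporting delay applies equally to a restart after Visit 2, 3 or 4, so the differences between visits stand. If the sponsor requires a confirmatory repeat, the time saved shrinks by the time the repeat takes.
- **The randomized withdrawal comparator is selective.** A placebo patient there, also without phosphate-lowering treatment, stops at a single value of 9. But that period is blinded, lasts up to 12 weeks and has visits every 14 days. Wash-out is shorter and monitored weekly, and the protocol enrolls patients at 9 to 10. In the 26-week period the hyperphosphatemia stops begin only after Week 2. These points stand; the comparison supports having some numeric stop, not a limit of 9.
- **Harm from one or two extra weeks is not shown, and other safeguards exist.** No passage quantifies such harm. Section 2.5 notes that hemodialysis patients are seen three times a week, which does not help those on peritoneal dialysis. These safeguards limit the severity of the gap but do not correct the instruction.

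**Conclusion.** The concern holds. For a patient above 10.0 mg/dL at Visit 2 or 3, the stated rule extends time off binders without serving the purpose of wash-out, and no numeric criterion overrides it before Visit 4. The scheduled cost is 7, 13 or 6 days, depending on the visits involved, assuming that the site follows Section 8.2 literally and nobody intervenes. The 13-day figure also assumes that the patient does not qualify at Visit 3.

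The number of patients affected is unknown; the probabilities above illustrate and are not evidence. Mitigation is real but partial: weekly s-P, the 4-week cap, investigator discretion and footnote h. Power, the primary analysis and the Day 1 and Visit 13 baselines are unaffected. This is a safety and site-consistency point that should be fixed, chiefly because the correction is small.

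**What to change.** In Section 8.2, restrict the move to the next visit to patients with s-P below 6.0 mg/dL or a rise under 1.5 mg/dL. Add that s-P above 10.0 mg/dL at any wash-out visit, confirmed on a prompt repeat if the sponsor prefers, is a screen failure and that binders are restarted under footnote h. Put the same threshold in footnote h. The two branches cannot overlap, because a value above 10.0 always means a rise of more than 2.0 mg/dL.

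The cost is one or two sentences, a matching footnote edit and a notice to sites. A few more patients would fail in wash-out, and for them the failure would be final, since Section 5.3 allows rescreening only after a Visit 1 failure on s-P. The prompt repeat limits losses from a single spurious value.
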